Wrinkles, in general, are reported to appear in people even younger than thirty years of age³. In the same manner as any other facial wrinkle, periorbital wrinkles increase gradually and affect one's appearance and facial expression. Such effect also reflects on quality of life, due to impact on social interactions, occupational functioning and self-esteem in general⁴. Therefore, periorbital wrinkle reduction treatments are sought by many worldwide.

Study Title:

A Prospective, Randomized, Double Arm, Controlled Study with Blinded Assessment To Evaluate The Safety And Effectiveness Of The Tixel Fractional System In The Treatment Of Periorbital Wrinkles In Comparison With Fractional Laser

Investigational Product:

Tixel by Novoxel, model No. TXLD0002

The Tixel system was designed to fulfill a clinical need for fractional treatment for aging skin with reduced side effects and safety related complications, associated with current available treatment modalities, together with increasing patient comfort. The Tixel employs a thermo-mechanical

¹ “A Prospective Split-Face Comparative Study of Periorbital Wrinkle Treatments: Fractional Erbium Doped Yttrium Aluminum Garnet Laser Intense Pulsed Light, and Topical 0.1% Tretinoin Cream”, So Eun Park, Sang Seok Kim, Chul Woo Kim, Young Her, Department of Dermatology, Kangdong Sacred Heart Hospital, Hallym University College of Medicine, Seoul,

¹Department of Dermatology, Kangwon National University Hospital, Kangwon National University School of Medicine, Chuncheon, Korea

² <https://www.mayoclinic.org/diseases-conditions/wrinkles/symptoms-causes/syc-20354927>

³ “Wrinkles”, Juan Manríquez, Daniela Majerson Grinberg, and Claudia Nicklas Diaz, Clinical Evidence 2008;12:1711

⁴ Gupta MA, Gupta AK. Photodamaged skin and quality of life: reasons for therapy. J Dermatol Treat 1996;7:261–264.

technology that has been designed to provide a comparable clinical effect as a pulsed laser, which can be used as a treatment modality for a variety of applications, including fractional treatment of human skin. The Tixel technology is based on the supply of contact-transferred heat from a high temperature (385°- 400°C) metal element (called a “tip”) consisting of an array of miniature pyramids. The tip creates a thermal effect in the tissue (usually 200-300 microns deep) in the tissue within 5 – 16 milliseconds, thus mimicking the pulsed laser action. The tip thermally generates a matrix of coagulation sites (or “micropores”) on the skin. Dermal heating and coagulative effect that occur during the treatment session provide for dermal remodeling and collagen restructuring that promote wrinkle reduction and general wrinkle appearance improvement.

Protocol Number:

CLN 0460

Study Design:

Prospective, single-blinded, randomized, controlled study

Number of Study Sites:

2

Study Population:

Male and female subjects between 40-70 years of age (inclusive) diagnosed with clinically evident periorbital wrinkles

Study Treatment:

Subjects will be treated with the Tixel for periorbital wrinkles every 4-6 weeks for a series of 3 to 5 treatment sessions followed by 3 follow up sessions (see flowchart for full schedule details and options). The number of treatments may vary from subject to subject and shall be determined by the investigators' assessment of the subjects' improvement.

The minimal estimation for study duration per subject is 27 weeks, and the maximal estimation is 47 weeks (please see study flowchart for further details).

Comparator Treatment:

The ResurFX Non-Ablative Laser with the M22 device by Lumenis (1565 nm) for treatment of periorbital wrinkles

2. STUDY OBJECTIVES:

To demonstrate the safety and performance of the Tixel fractional system for treatment of periorbital wrinkles in comparison to the selected market-cleared comparator.

2.1.Primary Outcome Endpoints:

Each subject shall be assessed based on FWCS. Each subject shall contribute two separate data time points to the study.

2.2.Safety

Physical and dermatological examinations, erythema, and adverse events (such as PIH, burns, etc.) monitoring will be performed and assessed at every visit (including follow up visits).

2.3.Effectiveness/Performance

Effectiveness/Performance shall be assessed and quantified by 3 blinded assessors.

The following assessment method will be applied by the blinded assessors (by images only):

- FWCS - Fitzpatrick Wrinkle Classification System

2.4.Secondary Outcome Endpoints

The following criteria will be assessed as secondary outcome endpoints:

- Secondary Effectiveness/Performance shall be assessed and quantified by a handling physician (one of the team's investigators of the study).

The following assessment methods will be applied (frontal clinical assessment or by images):

- FWCS - Fitzpatrick Wrinkle Classification System
- GAIS - Global Aesthetic Improvement Scale Assessment
- WAS - 5-point Wrinkle Assessment Scale
- Subject Experience
- Pain Level VAS Scale
- Subject Subjective Downtime Assessment

- Subject redness, edema and crust assessment (time for resolution)
- End-User Experience Assessment

Clinic Visits Baseline, 4wk, 8wk, (optional 12wk and 16wk), 20wk, 28wk, 42wk

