6. STUDY DESIGN

The study is designed to explore the safety and effectiveness of the Tixel, a novel fractional device, in treatment of periorbital wrinkles in comparison to a currently market-available product, which applies fractional treatment. The study is designated to compare between the effect of a currently available fractional pulsed laser modality (the "comparator"), market-cleared in the US for the said purpose, and the Tixel.

This is an interventional, double-arm, controlled, randomized, prospective, multi-center (US, Israel), clinical study with single-blinded evaluation. The Tixel treatment results will be compared to a laser modality indicated for the same purpose.

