11.2.1 Safety Assessment

Frequency and incidence of physical and dermatological examinations will be summarized.

Adverse events will be reported in tabulated format based on all ITT (intent to treat data set).

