11.3.1.1 FWCS - Fitzpatrick Wrinkle Classification System

11.3.1.2 GAIS - Global Aesthetic Improvement Scale Assessment

11.3.1.3 WAS - 5-point Wrinkle Assessment Scale

11.3.1.4 Subject Experience

11.3.1.5 Pain Level VAS Scale

11.3.1.6 Subject Subjective Downtime Assessment

11.3.1.7 Subject Response Questionnaire (redness, edema and crust - time to resolve)

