11.3.1.8 End-User Experience Assessment

11.3.1.9 Repeated measures or Friedman's test (as is appropriate) will be applied for analyzing the changes within side (device) and .The two-sample T-test or Non-parametric Mann-Whitney Rank test (as is appropriate) will be applied for comparative analysis of the changes between the devices.

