13 EXPECTED POSSIBLE SIDE EFFECTS (FOR BOTH DEVICES)

In the same manner as all fractional skin treatment devices, there is some risk of: Temporary swelling; Skin redness; Pain and/or burning sensation; Forming of large scabs or scabs lasting more than 15 days; Significant/thick skin peeling and/or peeling; Post Inflammatory Hyperpigmentation (PIH); Hypopigmentation; Sensitivity to sun exposure; Local burns; Scars; Local bacterial infection.

There is also the risk of loss of confidentiality. However, safeguards will be implemented to reduce this risk, including coding of data and images.

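### Section 2 aims to demonstrate safety relative to the laser, but adverse events such as PIH, burns and scars get only a table, with no between-device estimate or interval

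*Combined protocol and SAP*

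**What the plan says.** The single objective in section 2 is "To demonstrate the safety and performance of the Tixel fractional system for treatment of periorbital wrinkles in comparison to the selected market-cleared comparator". The study title uses the verb evaluate, and section 6 is softer still: "The study is designed to explore the safety and effectiveness of the Tixel". Section 2.2 describes the data to be collected: "Physical and dermatological examinations, erythema, and adverse events (such as PIH, burns, etc.) monitoring will be performed and assessed at every visit".

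The analysis is in two places.

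- **Adverse events and examinations, section 11.2.1.** The whole plan is two sentences: "Frequency and incidence of physical and dermatological examinations will be summarized", and "Adverse events will be reported in tabulated format based on all ITT (intent to treat data set"). No between-device difference, confidence interval, test, margin or success criterion is given.
- **Tolerability, section 11.3.** Pain VAS, downtime and the "Subject Response Questionnaire (redness, edema and crust - time to resolve") are secondary endpoints. Under 11.3.1.9 a two-sample t-test or Mann-Whitney test "will be applied for comparative analysis of the changes between the devices". No estimate or interval is named.

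Section 13 lists eleven expected reactions for both devices. Section 10 sizes the trial on FWCS improvement and contains no adverse-event rate, safety margin or safety power.

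**The concern.** A comparative safety objective needs a comparative quantity. For PIH, burns, scars, hypopigmentation and infection the plan yields counts but no statement of how far apart the devices could truly be. With few events, two similar columns can mean similar risk or too few subjects to tell, and a bare table does not separate the two. The document also uses three verbs of different strength for the same aim, so the reader cannot tell whether safety is to be shown against a standard or described. What is at stake is how much weight a clean-looking table can bear at the end of the trial.

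**Working it through.** **Inputs from the documents.** 41 recruited per group, 32 completers per group, FWCS margin 0.5, SD 0.8, 80% power, 20% dropout (section 10); reactions (section 13). **Assumptions.** The documents give no adverse-event rate and no safety margin, so every rate, margin and non-zero count below is illustrative.

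**1. The plan's own sample size.** n = 2(z₁₋α + z₀.₈)² SD²/margin² = 2 × (1.645 + 0.842)² × 0.64/0.25 ≈ 31.7, so 32 per group. Then 32/0.8 = 40, and the plan rounds up to 41. The figure reproduces at one-sided 5%. No safety quantity enters it.

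**2. Which reactions have no comparison.** Four of the eleven in section 13 (swelling, redness, pain, scabs) overlap endpoints tested under 11.3.1.9. An example is "Forming of large scabs or scabs lasting more than 15 days", which overlaps the crust-resolution endpoint. The other 11 − 4 = 7 do not: peeling, PIH, hypopigmentation, sun sensitivity, local burns, scars and local bacterial infection. For these seven the 11.2.1 table is the whole plan.

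**3. Zero events in both arms (no assumed rate needed).** With no events the Wilson upper limit is z²/(n + z²) = 3.84/(41 + 3.84) = 0.0857. The Newcombe 95% interval for 0/41 v 0/41 is therefore −8.6 to +8.6 points. For one arm, the exact two-sided upper limit is 1 − 0.025^(1/41) = 8.6%. If only 32 per arm were observed, it is 1 − 0.025^(1/32) = 10.9%.

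**4. A few events (assumed counts).** For 3/41 v 1/41 the Wilson limits are 2.5% to 19.4% and 0.4% to 12.6%, and the difference is 7.3 − 2.4 = 4.9 points. Newcombe:

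- lower: 4.9 − √[(7.3 − 2.5)² + (12.6 − 2.4)²] ≈ −6.4
- upper: 4.9 + √[(19.4 − 7.3)² + (2.4 − 0.4)²] ≈ +17.2

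**5. Chance of seeing a reaction at all in one arm,** 1 − (1 − p)⁴¹: 34% at a true rate of 1%, 56% at 2%, 88% at 5%.

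**6. Power to detect a difference (assumed rates).** Exact two-sided Fisher power at 41 per arm sums the two binomial probabilities over all tables with p ≤ 0.05.

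| Rates | Fisher power |
|---|---|
| 5% v 15% | 19% |
| 5% v 20% | 43% |
| 5% v 30% | 83% |

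**7. Power to exclude a margin (assumed equal rates p, margin m).** Normal approximation, one-sided 2.5%: Φ(m/SE − 1.96), with SE = √[2p(1 − p)/41].

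| p | SE | m = 10 points | m = 15 points |
|---|---|---|---|
| 5% | 0.048 | 55% | 88% |
| 10% | 0.066 | 33% | 62% |

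**The case against.** Descriptive reporting of adverse events is ordinary in a device trial of this size and is not in itself an error. The title and section 6 suggest nothing stronger was meant, and no safety hypothesis or margin appears anywhere. All of that stands. It makes this a matter of wording and missing precision, not a failed confirmatory analysis.

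Four stronger readings are tempting, and the documents do not support them.

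- *The table is the only planned safety analysis.* It is not, if tolerability counts as safety: pain, downtime and redness, edema and crust resolution are tested between devices under 11.3.1.9.
- *Forty-one per arm cannot demonstrate safety.* That depends on a rate and margin the documents do not give. At an assumed 5% rate, a 15-point margin would have 88% power.
- *Safety is a primary endpoint.* Section 2.1 names only FWCS, and 2.2 is a heading of the same level. The numbering of 11.2.1 under the primary performance endpoint is ambiguous, but no text calls safety primary.
- *The sponsor will conclude comparable safety from the table.* No sentence says so.

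A further fair objection is that intervals for every reaction would multiply comparisons and duplicate the tests in 11.3.1.9. The fix is limited for that reason.

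**Conclusion.** The point holds in a limited form and is a cheap improvement. The safety verb in section 2 is stronger than in the title and section 6. For the adverse events not covered by the tolerability endpoints, the plan names no between-device estimate, interval or margin. The trial was sized on FWCS only.

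The firmest figure is the best case: with 41 per arm and no events in either, a true difference of up to about 8.6 points in either direction is not excluded. That needs no assumed rate, only all 41 per arm in the analysis. The other figures (−6 to +17 points for 3 v 1; 43% power for 5% v 20%; 83% for 5% v 30%) rest on assumed counts and rates. They show that only large differences can be detected or excluded. They do not show that the design is incapable of supporting any safety statement.

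**What to change.** In section 11.2.1, for any adverse event and for each section 13 reaction not already compared under 11.3.1.9, report by device the number of subjects with at least one event, and the Tixel-minus-laser risk difference with a 95% interval (Newcombe, for example). By the count above that is 7 + 1 = 8 rows. State that these are estimates without multiplicity-adjusted testing, and cross-refer to 11.3.1.9 for the reactions handled there.

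In section 2, reword the safety part so that the aim is to evaluate or estimate the safety of Tixel relative to the comparator, in line with the title and section 6.

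The cost is one extra table and a more modest safety statement. No added subjects, visits or data collection are needed.

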8. STUDY BLINDING

This study is single blinded with limited access to the randomization code. Every effort will be made to retain the integrity of the blinding. Subjects will be randomized post-screening.

The treatment each subject shall receive will not be disclosed to any of the investigators until subject screening and enrollment is complete. The same shall apply regarding study site personnel, subjects, monitors, or the Sponsor staff except as required for the purposes of conducting this study.

The blinded evaluators shall not be exposed to the information, as well, in order to keep their assessment objective.

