9. STUDY FLOWCHART AND FOLLOW-UP ASSESSMENTS

Procedure	Visit 1	Visit 2	Visit 3	Visit 4	Visit 5	Visit 6	Visit 7	Visit 8
	Treatment 1 ^c	Treatment 2	Treatment 3	Treatment 4 Optional	Treatment 5 Optional	1 month Follow-up 1	3 months Follow-up 2	6 months Follow-up 3
	T ₀ ^f (± 5d) ± Δ ^{ef}	T ₀ + 4w (± 5d) ± Δ	T ₀ + 8w (± 5d) ± Δ	T ₀ + 12w (± 5d) ± Δ ^e	T ₀ + 16w (± 5d) ± Δ ^e	T ₀ + 20w (± 8d) ± Δ ^e	T ₀ + 28w (± 8d) ± Δ ^e	T ₀ + 42w (± 8d) ± Δ ^e
Max duration	-	4w+5d	8w+10d	12w+15d	16w+20d	20w+25d	28w+33d	40w+41d ~ 47w
Min duration	-	4w-5d	8w-10d	-	-	12w-15d	20w-23d	32w-29d ~28w
Subject Screening, Enrolment Procedure & Informed Consent ^g , Post treatment care instructions	X							
Facial dermatological skin examination	X	X	X	X	X	X	X	X
Inclusion/ Exclusion criteria	X							
Medical/Surgical history	X							
Demographics	X							
Limited Physical examination ^a	X							
Concomitant Therapy/Medication	X _b	X	X	X	X	X	X	X
Verbal Inquiry regarding pregnancy	X	X	X	X	X	X	X	X
Photography of Treatment Area(s) – prior to treatment	X (baseline)	X	X	X	X	X	X	X
Photography of Treatment Area(s) – After treatment			X					
Investigational/Comparator Device Treatment	X	X	X	X	X			
Subject experience and satisfaction questionnaire	X		X*	X*	X*	X*		X

Procedure	Visit 1	Visit 2	Visit 3	Visit 4	Visit 5	Visit 6	Visit 7	Visit 8
	Treatment 1 ^c	Treatment 2	Treatment 3	Treatment 4 Optional	Treatment 5 Optional	1 month Follow-up 1	3 months Follow-up 2	6 months Follow-up 3
GAIS Assessment		X	X	X	X	X	X	X
FWCS Assessment	X _f	X	X	X	X	X	X	X _f
WAS Assessment	X _f	X	X	X	X	X	X	X _f
Subject VAS Pain assessment	X	X	X	X	X			
Subject Assessment Questionnaire (regarding downtime, skin erythema, redness and scabs)		X	X	X	X	X		
Adverse Events	X	X	X	X	X	X	X	X
Subject Compliance	X	X	X	X	X	X	X	X
Post Treatment Care Instructions	X	X	X	X	X			

- A limited physical examination will be performed at Screening to support the eligibility determination. System review will include general appearance, and a routine physical examination, according to the standard of care and as customary for fractional treatments.
- At Screening, the review of concomitant medications should include those taken within the past year.
- All assessments on treatment days are to be performed prior to treatment; the assessments performed prior to Treatment 1 will be designated as Baseline.
- Treatment sessions 4 & 5 are optional for both treatment options, based on the investigator's assessment of the subject's response.

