- The sign Δ signifies the possibility of the change of the study's duration. Any delay of this sort will be documented and explained in writing.
- Blinded assessment performed in addition to physician assessment. Shall be performed at the end of the subject's activities.
- First visit may be split into two separate visits: part I: screening, enrollment and informed consent, and part II: rest of visit content (see in **שוויה! מקור ההפניה לא נמיצה.**)

* The * symbol is designated to show that filling out the Subject experience and satisfaction questionnaire is optional and should only be performed in one of the visits marked by the symbol. This is because it may be determined in a specific treatment visit (no. 4 or no. 5) that no more treatments are required. Therefore, the questionnaire

should be filled out in the last treatment visit or in a following visit. For convenience purposes, it is also allowed to have the questionnaire filled out by the subject in the first follow-up visit.

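### Secondary WAS is compared between devices on scores from a physician who very probably knows the device, although the flowchart appears to schedule blinded WAS and section 11.3 does not say which score is analysed

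*Combined protocol and SAP*

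**What the plan says.** All references are to the combined protocol and SAP.

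- **Blinded raters (2.3 and the start of 2.4).** "Effectiveness/Performance shall be assessed and quantified by 3 blinded assessors". The method is introduced with "The following assessment method will be applied by the blinded assessors (by images only"), and FWCS is the only scale listed.
- **Secondary raters (2.4).** "Secondary Effectiveness/Performance shall be assessed and quantified by a handling physician (one of the team's investigators of the study"). The scales include FWCS, GAIS and WAS. On how they are scored: "The following assessment methods will be applied (frontal clinical assessment or by images"). Nothing says which mode applies when.
- **Blinding (8).** "This study is single blinded with limited access to the randomization code". The allocation "will not be disclosed to any of the investigators until subject screening and enrollment is complete". The only people whom the section keeps unaware beyond that point are the blinded evaluators.
- **Flowchart (9).** The row "WAS Assessment" carries the mark f at Visits 1 and 8, as does the FWCS row. The GAIS row has no such mark and no Visit 1 entry. The sixth footnote begins "Blinded assessment performed in addition to physician assessment".
- **Analysis (11.3).** FWCS, GAIS and WAS are listed as secondary endpoints, and changes are compared between devices by a two-sample t-test or Mann-Whitney test. No rater is named.

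**The concern.** A subjective wrinkle grade given by someone who knows the device can drift toward the device that the rater expects to do better. A test between devices cannot separate that drift from a real effect. Here the rater is also one of the investigators, and investigators decide from their own view of improvement whether a subject has a fourth or fifth session. They will therefore often hold an opinion of the response before they score it.

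For WAS this exposure looks avoidable, because the flowchart appears to schedule a blinded reading at the two visits that matter. As the text stands, 2.4 sends the WAS comparison to the physician, the flowchart suggests that a blinded WAS will also exist, and 11.3 does not choose between them. The choice could then be made after both sets of scores are known.

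A smaller matter is that the physician may score live at one visit and from images at another. A change score can then contain a difference between modes.

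**Working it through.** **1. Is the handling physician masked?** Section 2.4 makes this rater an investigator. Section 8 ends concealment from investigators once screening and enrolment are complete, and describes the study as single-blinded. No sentence says outright that the physician knows the device, and none masks the physician at later visits. Awareness is therefore a strong inference rather than a stated fact.

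**2. Is blinded WAS scheduled?** In the text available, the flowchart footnotes carry no letters. Read in order, the first is the limited physical examination (a), the second concomitant medication (b), the third baseline (c), the fifth the delta sign (e) and the seventh the split first visit (g). Each fits the mark seen in the table, so the sixth, on blinded assessment, is f. One f, on the T0 column header, is not explained by this reading. It does not bear on the WAS row.

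**3. Side by side.**

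| Scale | Blinded, by 2.3/2.4 | Blinded, by flowchart | Rater named in 11.3 |
|---|---|---|---|
| FWCS | yes (primary) | Visits 1 and 8 | none |
| WAS | no | Visits 1 and 8 | none |
| GAIS | no | no | none |

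Only the WAS row is in conflict.

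**4. The plan's own sample size.** Section 10 uses a margin of 0.5, SD 0.8 and 80% power. With a true difference of 0 and one-sided 5%:

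n = 2 × (0.8/0.5)² × (1.645 + 0.842)² ≈ 31.7, so 32 per arm; 32/0.80 = 40; the plan recruits 41.

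The stated figures reproduce, and nothing in this point changes them. They supply the range of n used below.

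**5. Illustration of observer bias.** Assume no true device difference and a rater who favours one device by d standard deviations. In a two-sided 5% test (normal approximation) the statistic is shifted by d/√(2/n), and the false-positive rate is P(|Z + shift| > 1.96).

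- d = 0.2, n = 32: shift = 0.2/0.25 = 0.80; rate 12.6%.
- d = 0.2, n = 41: shift = 0.2/0.221 = 0.91; rate 14.8%.

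The documents give neither a bias figure nor an SD for WAS or GAIS. The table below varies the lean, using the FWCS SD of 0.8 to convert SD units to points.

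| Assumed lean | n = 32 | n = 41 |
|---|---|---|
| 0 | 5% | 5% |
| 0.1 points (0.125 SD) | 7.9% | 8.7% |
| 0.16 points (0.2 SD) | 12.6% | 14.8% |
| 0.25 points (0.31 SD) | 24.0% | 29.3% |
| 0.5 points (0.625 SD) | 70.5% | 80.8% |

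The assumed lean, not n, drives the result.

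**6. Scoring mode.** If live and image scores differ by some amount and the mode mix is the same in both arms, the difference adds variance to physician FWCS and WAS changes but does not shift the device comparison. It shifts the comparison only if the mix differs by arm, and nothing in the documents says that it will. GAIS has no Visit 1 score to subtract, so the argument does not apply to it in the same way.

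**The case against.** The strongest reply is that the plan already protects what matters. Effectiveness on FWCS is judged by three blinded assessors from images, and 11.2 analyses it as the primary endpoint. Physician ratings are openly labelled secondary, and open ratings beside a blinded primary are a disclosed design choice. This stands, and it limits the point to secondary endpoints.

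Four stronger readings are tempting, and the documents do not support them.

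- *A mixed live and image change could consume the non-inferiority margin.* The margin belongs to the primary comparison, whose scores come from images at both ends. Mode mixing cannot enter it.
- *Blinded WAS is being collected and thrown away.* Its collection is inferred from a footnote read by order. Section 11.3 names no rater and does not exclude it.
- *The plan states that the physician is unblinded.* It does not; this follows from section 8 and the rater's role.
- *Blinded GAIS has been forgotten.* The GAIS row has no f mark, so a blinded GAIS would be an addition, not a reconciliation.

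The reply does not remove the WAS conflict. Section 2.4 as written gives the WAS comparison to a rater who is probably aware of the device, while the flowchart points to a masked alternative.

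**Conclusion.** The point holds for the secondary endpoints. Physician FWCS, WAS and GAIS comparisons between devices are open to observer bias. For WAS, sections 2.3/2.4 and the flowchart disagree on whether the blinded assessors score it, and 11.3 leaves the analysed score unspecified. The primary FWCS conclusion and the sample size are untouched.

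The size of the bias cannot be derived from the documents. At an assumed lean of 0.2 SD the false-positive rate per endpoint would be about 13% to 15% instead of 5%. The conclusion rests on two inferences: that the handling physician knows the device, and that mark f is the blinded-assessment footnote. Even a reader who expects a negligible lean has reason to settle which WAS score is analysed before the data are seen.

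**What to change.** - **2.3/2.4:** add WAS to the blinded assessors' list, scored from images at baseline and Visit 8, to match the flowchart.
- **11.3:** name the blinded WAS change from baseline to Visit 8 as the between-device WAS comparison, with the three assessors' scores combined in the same way as for the primary FWCS.
- **11.3:** label the physician's FWCS, WAS and GAIS comparisons as supportive and open-label.
- **2.4:** require one mode, live or image, for all of the physician's scores.
- **Optional:** have the blinded assessors rate GAIS from the same image pair after their FWCS and WAS scores are locked.

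The cost is wording plus some rating time. If every assessor rates every subject, WAS needs 82 × 2 × 3 = 492 ratings, or six per subject, on photographs already scheduled. If the flowchart states the intent, these ratings are already planned. No extra subjects or visits are needed.
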